1.1.2. Clinical Phenotype of K_{ATP} Hyperinsulinism

$K_{ATP}HI$ is characterized by large for gestational age birth weight (due to stimulation of fetal growth by excessive insulin *in utero*), neonatal onset of hypoglycemia, and unresponsiveness to diazoxide therapy. In addition to fasting hypoglycemia, children with $K_{ATP}HI$ have protein-induced hypoglycemia (18). Most reported K_{ATP} channel mutations are recessive, however a few dominantly expressed mutations have been reported (19-21). The dominant defects retain responsiveness to diazoxide and tend to be milder.

There are at least two distinct histological forms of $K_{ATP}HI$, diffuse hyperinsulinism and focal hyperinsulinism. In focal hyperinsulinism (approximately 40-60% of all cases) a somatic reduction to homozygosity (or hemizygosity) of a paternally inherited mutation of *ABCC8* or *KCNJ11* and a specific loss of maternal alleles of the imprinted chromosome 11p15 region result in a focal lesion. Pre-operative identification and localization of these focal lesions by ¹⁸F-fluoro-L-DOPA facilitates local resection of the lesion and cure of this form of hyperinsulinism (22-24). Infants with diffuse hyperinsulinism require a near-total pancreatectomy (98%) to control the hypoglycemia and often require additional therapy with octreotide, and/or frequent feedings to maintain euglycemia. At The Children's Hospital of Philadelphia's Congenital Hyperinsulinism Center, the largest center in this country caring for children with disorders of insulin regulation, we evaluate and treat approximately 20-30 infants with medically-unresponsive hyperinsulinism requiring pancreatectomy every year. Among cases with diffuse hyperinsulinism, approximately 54% had persistent hypoglycemia after a near-total pancreatectomy, up to 24% required a second pancreatectomy for persistent hypoglycemia, 18% had persistent hypoglycemia but were medically controlled, and 20% had insulin-requiring diabetes. Thirty-one percent of the cases had surgical complications, including bowel obstruction, pancreatic exocrine insufficiency, necrotizing enterocolitis and death (1 from necrotizing enterocolitis and 1 from bowel obstruction).

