1.2.3. Toxicity

Exendin-4, the naturally occurring *Heloderma* product, has been used extensively in human studies (83-85). Side effects reported with exendin-4 have been limited, although in higher doses nausea has been reported. Exendin-(9-39) is a synthetic molecule that has also been used in multiple human studies (79; 81; 86-91). Dose ranging studies have been reported by both Schirra and Edwards (79; 81). In neither of the previous studies were adverse effects of exendin-(9-39) reported. In addition, no effects of exendin-(9-39) on blood pressure and heart rate were found on these studies. In both animals and humans studies exendin-(9-39) seems to be relatively short-lived in the circulation. While GLP-1 seems to play an important role in glucose tolerance it is not the only regulatory factor involved, and the glucose tolerance induced by exendin-(9-39) is relatively modest. In our studies, infusion of exendin-(9-39) to mice with a null mutation of the K_{ATP} channel did not significantly worsen the glucose tolerance of these mice, nor affected weight gain (16). We have not observed any serious adverse events on the subjects we have studied under this IND: to date, all doses appear to have been generally safe and well tolerated in all three populations studied. There have been no SAEs, deaths, or withdrawals due to study drug.

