We developed a specific and sensitive LC-MS/MS method to quantify the concentration of exendin-(9-39) in human plasma (82) and measured exendin(9-39) concentration serially in individuals who participated in our research studies and received exendin-(9-39) intravenously. A total of 202 PK observations from twenty-six adult and pediatric subjects were included in the analysis. The final parameter estimates were obtained using FOCE with interaction method in NONMEM (version 7.3). A linear two-compartment model best described the observed data, and the PK parameters were estimated with good precision (%CV<50). The PK parameters were related to body weight and age. Gender and creatinine clearance did not affect the clearance of exendin-(9-39) in the studied population. Typical clearance and elimination half-life for pediatric population with median weight 5 Kg are 1.64 L/hr and 0.94 hr, respectively.

The final model parameters are presented in the table below:

PARAMETERS	Population Mean (SE)	Population Variance (%CV)
CL (L/hr)	11.9 (0.781)	0.0722 (0.0309)
VC (L)	8.57 (0.925)	-
Q (L/hr)	3.85 (1.36)	-
Vp (L)	7.00 (1.24)	-
σ _Proportional error	0.310 (0.0381)	-

Based on our clinical data to date including the observed and modeled PK data, we are proposing additional dose-escalation cohorts starting with a dose that is 2-fold higher than the highest dose used in the pilot study [1000 pmol/kg/min (0.2 mg/kg/hr)] up to a maximum dose that is lower than the human equivalent (assuming 70% bioavailability) NOAELs from the toxicology studies in rats and dogs. The estimated range of AUC (A) and C_{Max} (B) with these doses were simulated using the developed population PK model and are shown as follows:

The dotted line is the exposure of the NOEL dose in dog. The dashed line is the exposure of the NOEL dose in rat. AUC0-inf = Area under the concentration-time curve from time=0 to infinity; Number of simulated subject = 1000; Open circle = Median; Error Bar = 95 % percentile

Clinical and nonclinical pharmacokinetic parameters and safety factors are summarized in the following table.

Study Type	Dose (mg/kg/hr)	C_{max} (ng/mL)	AUC (ng*hr/mL)
Proposed in Neonates	0.2	69.45 ^a	625.5 ^a
Proposed in Neonates	0.6	208.3 ^a	1876 ^a
Proposed in Neonates	2	694.5 ^a	6255 ^a
Proposed in Neonates	6	2083 ^a	18764 ^a

Rat (Study #13835B)	900 mg/kg/day (300 mg/kg TID)	63200 ^b	249,000
Dog (Study #13835D)	300 mg/kg/day (100 mg/kg TID)	49500 ^c	340,500

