6. Feedings: Infants will be allowed to continue feedings by mouth or by nasogastric/gastrostomy tube. Feedings will be continued every 3 hours and the volumes offered will be maintained equal during the two 9 hr study

- periods. The volume taken with each feeding will be recorded. Only intravenous glucose will be adjusted to maintain euglycemia.
7. Randomization: The investigational drug services will assign the order of the studies by randomization. They will inform the PI, study coordinator, and CTSC.
 8. Intravenous infusion of exendin-(9-39) and vehicle. All subjects will receive an infusion of exendin-(9-39) and vehicle for 9 hours on two separate days and in random order. Exendin-(9-39) /vehicle will be infused intravenously over a period of 9 hours starting at approximately the same time \pm 90 minutes on each day. The starting dose of exendin-(9-39) will be 1000 pmol/kg/min (0.2 mg/kg/hr). The dose will be escalated as outlined below. The volume of saline to be infused will be calculated to match the volume rate of exendin-(9-39).
 9. Post-infusion follow-up for subjects who have been able to discontinue dextrose infusion. Subjects who have been able to discontinue the dextrose infusion and who are not on supplemental dextrose infusion at the end of the study will continue to be monitored without additional dextrose infusion for up to 3 hours after the end of the study drug infusion, or until blood glucose is $<$ 70 mg/dL (whichever comes first). In addition to blood glucose monitoring every 30 minutes and betahydroxybutyrate every 1 hr from a capillary sample, a venous sample will be drawn at the end of 3 hours (or when blood glucose $<$ 70 mg/dL, whichever comes first) for plasma insulin and glucose.
 10. Dose schemes.

Scheme #1 (completed as of date of Protocol Amendment 7): exendin-(9-39) infused for 12 hrs at a dose of 100 pmol/kg/min (0.02 mg/kg/hr).

Scheme #2 (completed as of date of Protocol Amendment 7): exendin-(9-39) infused for 12 hrs at a dose of 200 pmol/kg/min (0.04 mg/kg/hr).

Scheme #3 (completed as of date of Protocol Amendment 7): exendin-(9-39) infused for 6 hrs at a dose of 500 pmol/kg/min (0.1 mg/kg/hr).

Scheme #4 (new as of date of Protocol Amendment 7): Dose escalation will be done as described below:

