 - a. Cohorts 1-2: at least 3 and up to 6 subjects per cohort, will be included in each of the first two cohorts. In any of the first 2 cohorts, if discontinuation of intravenous dextrose is achieved in 2 out of the 3 subjects up to three additional patients (at least 2 with diffuse disease, as defined by PET scan and/or genetics) may be enrolled in order to meet the Success Stopping Criteria (see 11a below).
 - b. Cohorts 3- 4: four subjects, with at least 2 subjects with diffuse disease. If discontinuation of intravenous dextrose is achieved in 1 or 2 of the 4 subjects, an additional subject with diffuse may be enrolled in order to meet the Success Stopping Criteria (see 11a below).

- c. The dose will be increased in $\frac{1}{2}$ log increments between cohorts as specified below:

Group	Dose Scheme (mg/kg/hr for 9 hours)	Total Dose (mg/kg)	Number of Subjects
1	0.2	1.8	3-6
2	0.6	5.4	3-6
3	2	18	3-5
4	6	54	4-6

11. Stopping Criteria:

- a. Success Stopping Criteria: the dose escalation will be stopped if in a cohort at least 2 subjects with diffuse disease are able to have dextrose infusion discontinued for the final 2 hours of the study period.
- b. Safety Stopping Criteria: if an exaggerated pharmacology effect is observed (blood glucose greater than 200 mg/dL for 2 hours off dextrose infusion) dose escalation will be stopped and the dosing algorithm will be modified to proceed with a dose that is 2 fold higher the previous level observed to be safe. Dosing will be stopped if any severe adverse event is observed.

12. Calculation of glucose infusion rate. Glucose infusion rate over the last 2 hours of the treatment period will be calculated by adding the total amount of intravenous glucose (in mg) received over 2 hours divided by the weight in Kg and by time (120 min).

13. Determination of therapeutic plasma levels, plasma half-life and pharmacokinetics of exendin-(9-39). During the infusion with exendin-(9-39) blood samples will be obtained at 1, 5, and 9 hours, and at 1 and 3 hours after the infusion ends. Should there be difficulty in establishing blood drawing lines to obtain samples of the secondary outcome variables the study will proceed with collection of the primary outcome variable only (glucose infusion rate). Plasma levels of exendin-(9-39) will be determined by mass spectrometry.

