The goal of this study is to find the intravenous dose of exendin-(9-39) (and the plasma concentration) that is necessary to completely abolish the need for exogenous glucose administration to maintain normal blood glucose in children with congenital hyperinsulinism. The sample size of three for each dosing regimen is a sample of convenience and not based on statistical considerations. However, we offer the following considerations based on our previous studies: for the first 9 subjects studied under this protocol the mean \pm standard deviation (SD) baseline glucose infusion rate (GIR) was 13.2 ± 4.8 mg/kg/min. Our hypothesis is that exendin-(9-39) will decrease the glucose infusion rate required to maintain blood glucose > 70 mg/dL. A paired test is called for to compare the two conditions – exendin-(9-39) and vehicle; however, since we do not actually know the SD of differences, our sample size calculation is based on the more conservative t-test for independent samples, and we use the SD of 4.8 as an estimate of the common SD; using a two group t-test with a 0.05 two-sided significance level.

Reduction in GIR	Sample size for 80% power	Sample size for 90% power
25%	34	45
50%	9	12
100%	3	4

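### Section 3.4: item 10b states no expansion for 3 of 4 responders when only one is diffuse, and item 11b gives no lower dose after a cohort 1 trigger (minor)

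*Combined protocol and SAP*

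**What the plan says.** Section 3.4 sets out the new escalation (Scheme #4) at 0.2, 0.6, 2 and 6 mg/kg/hr, each infused for 9 hours.

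- **Expansion, cohorts 3 and 4 (item 10b).** Each starts with four infants, and at least two must be diffuse cases. The expansion rule reads: "If discontinuation of intravenous dextrose is achieved in 1 or 2 of the 4 subjects, an additional subject with diffuse may be enrolled". Its stated purpose is to satisfy item 11a.
- **Success (item 11a).** Escalation stops if in a cohort "at least 2 subjects with diffuse disease are able to have dextrose infusion discontinued for the final 2 hours".
- **Safety (item 11b).** Blood glucose above 200 mg/dL for 2 hours off dextrose stops escalation, and the algorithm is then "modified to proceed with a dose that is 2 fold higher the previous level observed to be safe".
- **Table under item 10c.** It lists 3-5 subjects for group 3 and 4-6 for group 4. The text of 10b gives four, plus at most one.

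Section 1.4 describes the new cohorts as "starting with a dose that is 2-fold higher than the highest dose used in the pilot study". That highest dose was 0.1 mg/kg/hr for 6 hours (Scheme #3, section 3.4). Section 1.2.3 says of experience to date that "all doses appear to have been generally safe and well tolerated in all three populations studied". Section 3.5 states what the study sets out to do: "find the intravenous dose of exendin-(9-39) (and the plasma concentration) that is necessary to completely abolish the need for exogenous glucose". Section 5.4 leaves each decision to escalate or halt to the investigator, the Safety Officer and the pharmacologist, on review of safety data.

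**The concern.** Items 10b and 11a count different things. The expansion trigger counts responders of any disease type; the success rule counts diffuse responders only. A cohort can therefore do too well to qualify for expansion while still being one diffuse responder short of success. The weaker result, one responder of four who happens to be diffuse, does qualify.

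Item 11a is the rule that declares the study's goal reached, so a missed expansion can leave an effective dose undeclared. If that happens in cohort 3, item 11a does not stop escalation to 6 mg/kg/hr. If it happens in cohort 4, the study ends with 11a unmet at the last dose.

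Item 11b has a separate fault. Its evident intent is to step down after an exaggerated effect, and in cohort 1 it does not.

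**Working it through.** **Inputs.** Cohort composition and triggers: items 10b, 11a and 11b. Dose levels: the item 10c table and Scheme #3. Safety margins: the section 1.4 table. The protocol states no response rate, so rates below are assumptions. The section 3.5 sample-size table concerns mean glucose infusion rate and does not bear on these rules.

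**1. Which outcomes are missed.** Let d be the diffuse and f the focal responders among four. Success needs d ≥ 2. Item 10b allows expansion when d + f is 1 or 2. One extra diffuse responder can rescue the cohort only if d = 1. The missed outcome is therefore d = 1 with d + f ≥ 3.

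- 2 diffuse + 2 focal: d = 1, f = 2 is missed. It is the only such outcome.
- 3 diffuse + 1 focal: three responders include at least two diffuse, so 11a is already met. None missed.
- 4 diffuse: none missed.

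**2. Probability in a 2 + 2 cohort.** Assume independent responses with a common rate p, and that every permitted expansion is used.

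- Missed = 2p(1−p) × p²
- Success as written = p² + p × 2p(1−p)(1−p²)
- Success if the gap is closed = p² + p × 2p(1−p)

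| p | Missed | Success as written | Gap closed | Loss |
|---|---|---|---|---|
| 0.25 | 0.023 | 0.150 | 0.156 | 0.006 |
| 0.50 | 0.125 | 0.438 | 0.500 | 0.063 |
| 0.75 | 0.211 | 0.686 | 0.844 | 0.158 |

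With different rates pd (diffuse) and pf (focal), the loss is pd × 2pd(1−pd)pf² = 2pd²(1−pd)pf². Over 0.25 to 0.75 for each:

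- Smallest, at pd = pf = 0.25: 2 × 0.0625 × 0.75 × 0.0625 = 0.006.
- Largest, at pd = 2/3, pf = 0.75: 2 × 0.444 × 0.333 × 0.5625 = 0.167.

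**3. What a miss in cohort 3 could lead to.** The section 1.4 margins at 2 mg/kg/hr are 5.6-6.5 by dose and 40-54 by AUC. At 6 mg/kg/hr they are 1.9-2.2 and 13-18.

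**4. The item 11b fallback.** Section 1.4's own ratio checks: 0.2 / 0.1 = 2. Applying twice the preceding level to each cohort:

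| Cohort | Triggering dose | Fallback | Reduction |
|---|---|---|---|
| 1 | 0.2 | 2 × 0.1 = 0.2 | 0% |
| 2 | 0.6 | 2 × 0.2 = 0.4 | 33% |
| 3 | 2 | 2 × 0.6 = 1.2 | 40% |
| 4 | 6 | 2 × 2 = 4 | 33% |

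The rule works in cohorts 2 to 4. In cohort 1 it returns the triggering dose. If only Scheme #4 levels count, there is no previous level and the rule is undefined.

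**The case against.** The strongest reply is that these are narrow gaps that clinical judgment would fill. The first needs one exact composition and one exact outcome. Item 10b is permissive and does not say that expansion is allowed only in the listed cases; the table has room for a fifth infant in both groups. Section 5.4 puts people between one cohort and the next. Much of this stands, and it is why the point is minor. It does not remove the fault: the table conflicts with 10b and adds no trigger, and the section 5.4 review looks at safety and supplies neither an expansion rule nor a fallback dose.

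A reader might infer several stronger things that the documents do not support:

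- *That a missed expansion sends infants to 6 mg/kg/hr.* Only a miss in cohort 3 can lead there, because cohort 4 is the last level, and only if the section 5.4 reviewers choose to escalate. Item 11a says when escalation stops; nothing says it must otherwise proceed. The added diffuse infant would also have had to respond, so the lost success, not the larger probability of a missed expansion, is the relevant figure.
- *That item 10b forces pointless enrollment when only focal infants respond.* That expansion cannot reach 11a, but it is allowed, not required.
- *That item 11b exposes cohort 1 infants to a dangerous repeat dose.* The trigger looks unlikely there: section 1.4 reports no effect on glucose infusion rate in 2 neonates given 0.1 mg/kg/hr over 6 hours. The repeated dose would be the lowest in Scheme #4, with margins of 57-65 by dose and 398-544 by AUC, and glucose is checked every 30 minutes. Against that, section 1.4 also reports possibly related transient Grade 3 hyperglycemia in 2 of 31 treated subjects, doses not given, so the case is not empty.

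A third reading of 11b would disregard the 6-hour Scheme #3 as a safe level for a 9-hour infusion and give 2 × 0.04 = 0.08 mg/kg/hr. The text does not say this, and it sits badly with the statements in sections 1.2.3 and 1.4 that earlier doses were well tolerated.

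**Conclusion.** Minor, and wrong as written on both counts.

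The expansion gap is certain as a matter of wording. Its size is not: the 0.6 to 16.7 percentage points of lost success apply to a 2 + 2 cohort only, and rest on assumed rates of 0.25-0.75, independent responses and full use of permitted expansions. With more than two diffuse infants the loss is zero. The protocol does not say how often a 2 + 2 cohort would be enrolled; it is the minimum diffuse count that 10b sets.

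The item 11b fault needs no assumed rate. Neither natural reading gives a lower dose in cohort 1, though the event that would expose it looks unlikely.

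Neither fault touches the primary comparison of glucose infusion rate between exendin-(9-39) and vehicle.

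**What to change.** - **Item 10b.** Replace the trigger with: *If exactly one diffuse-disease subject meets the 11a response, one additional diffuse-disease subject may be enrolled.* This closes the gap and also drops expansions that cannot reach 11a.
- **Table under item 10c.** Set groups 3 and 4 to 4-5 subjects, to match the text of 10b.
- **Item 11b.** Name what happens after a cohort 1 trigger: for example about 0.13 mg/kg/hr (0.2 × 2/3, the same one-third reduction as in cohorts 2 and 4), a return to 0.1 mg/kg/hr, or a statement that dosing stops. Requiring merely a dose below 0.2 would not be enough, since it still names none.

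The cost is amendment wording. With the table aligned, Scheme #4 enrolls 3 + 3 + 4 + 4 = 14 to 6 + 6 + 5 + 5 = 22 subjects, against 13 to 23 from the current table. That remains in line with the approximately 20 additional subjects planned in section 3.3.

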1.4. Dose Rationale and Risk/Benefits

The doses used in previous human studies ranged from 30 to 900 pmol/kg/min (0.006 to 0.18 mg/kg/hr) (79; 81; 86-91). Schirra et al.(79) demonstrated that

under physiological post-prandial plasma levels of GLP-1 (achieved by an intravenous infusion) administration of exendin-(9-39) at 30 and 60 pmol/kg/min (0.006 and 0.012 mg/kg/hr) significantly reduced the glucose infusion rate required to maintain blood glucose at 140 mg/dL in normal subjects, while a dose of 300 pmol/kg/min (0.06 mg/kg/hr) totally abolished the elevated demand for exogenous glucose under the experimental conditions. Furthermore, at euglycemia, infusion of exendin-(9-39) at 300 pmol/kg/min (0.06 mg/kg/hr) significantly raised basal glucose and glucagon. Edwards et al.(81) studied the effect of exendin-(9-39) on fasting plasma glucose in normal adult volunteers. They found that exendin-(9-39) infused at a dose of 500 pmol/kg/min (0.1 mg/kg/hr) increased fasting plasma glucose significantly compared with controls infused with saline. After cessation of exendin-(9-39) infusion, the plasma glucose level in response to exendin-(9-39) dropped to that of the control. In summary, these studies demonstrated that at a dose of 300 pmol/kg/min (0.06 mg/kg/hr), exendin-(9-39), abolishes the effects of physiologic post-prandial plasma levels of GLP-1, and that a higher dose of 500 pmol/kg/min (0.1 mg/kg/hr) increases fasting plasma glucose levels in normal subjects. In these studies, exendin-(9-39) was well tolerated by all subjects and there was not effect on pulse or blood pressure. No adverse effects related to exendin-(9-39) were reported in the previously discussed studies.

[figure not shown]
In our studies in mice with a null mutation of SUR-1, a pilot study demonstrated that a dose of 150 pmol/kg/min (0.03 mg/kg/hr) was effective in increasing fasting blood glucose levels, while a lower dose of 50 pmol/kg/min (0.01 mg/kg/hr) did not have an effect. In our pilot human studies, we have used a dose ranging from 100-500 pmol/kg/min (0.02-0.1 mg/kg/hr). From these studies the higher dose (500 pmol/kg/min) was given at the end of the infusion elevating blood glucose levels after a long fast (18 hrs). These doses were well tolerated. We have studied 2 neonates at this dose level administered over 6 hrs and did not find an effect on glucose infusion rates.

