^a – median value of 1000 simulated subjects; ^b – represented Cmax value of male rats following a single dose administration; ^c – represented Cmax values of female dogs on Day 28

Safety Margins based on dose and exposure (AUC)

Proposed dose rate (mg/kg/hr)	Total dose over 9 hours ^a (mg/kg)	Safety margin based on HED from rat (300 mg/kg/day) ^b	Safety margin based on HED from dog (900 mg/kg/day) ^b	Safety margin based on Cmax from rat (63200 ng/mL) ^c	Safety margin based on Cmax from dog (49500 ng/mL) ^d	Safety margin based on AUC from rat (249000 ng*hr/mL)	Safety margin based on AUC from dog (340500 ng*hr/mL)
0.2	1.8	57	65	910	713	398	544
0.6	5.4	18	22	303	238	133	181
2.0	18	5.6	6.5	91	71	40	54
6.0	54	1.9	2.2	30	24	13	18

^a – Assuming infusion over nine hours is the daily dose

^b – For rat HED is 102 mg/kg/day; for dog HED is 117 mg/kg/day; calculations includes bioavailability of 70%

^c – represented Cmax value of male rats following a single dose administration; ^d – represented Cmax values of female dogs on Day 28

Exendin -(9-39) will be administered intravenously as in the previous human studies. In short-term infusions studies Schirra (79) and Edwards (81) did not find a cumulative or persistent effect once the infusion was discontinued. No adverse effects of exendin-(9-39) were reported in the previously discussed studies. Exendin-(9-39) was well tolerated by all subjects and there was not effect on pulse or blood pressure.

In the children, adolescents and adults with congenital hyperinsulinism that we have studied to date, all doses appear to have been generally safe and well tolerated in all three populations studied. There have been no SAEs, deaths, or withdrawals due to study drug. Adverse events, regardless of causality, were reported in 19 of the 31 subjects (61.3%) treated to date. Treatment-related AEs were reported in only 3 subjects (9.7%). The most common adverse event observed as expected in this population was hypoglycemia (16 of 31 subjects, 51.6%); the majority of these events were Grade 1 or 2 and all were assessed as unrelated to investigational drug. Adverse events possibly related to the investigational drug included emesis (Grade 1) in one subject and transient hyperglycemia in two subjects (Grade 3). The occurrence of adverse events was balanced between the investigational drug and vehicle conditions.

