5.4. Dose Escalation Decisions

Treatment cohorts will be dosed in escalating order as outlined above (section 3.4). Dose escalation decisions will be made by the investigator only after the safety of the previous dose level has been established. Subsequent cohorts will not be dose until safety data are obtained from all subjects in the previous cohort. Safety will be evaluated based on the incidence and severity of adverse events (AEs), clinical laboratory test results, ECGs, and other relevant clinical findings (e.g., heart rate, blood pressure, respiratory rate and temperature). Decisions to dose escalate or halt dose escalation will be based on review of these data by the investigator, the Safety Officer and the pharmacologist.

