5.5. Stopping Rules

Subject Specific Stopping Rules

All subjects will be monitored during administration of the investigational product and if any of the events below occur the subject will be discontinued from treatment and followed clinically.

1. Subjects who have a wheal and flare reaction in the 30 minutes following peptide injection for the Hypersensitivity Test will be withdrawn from further investigation due to a positive hypersensitivity test and any further research procedures will be canceled.
2. **Peptide stopping rules:** Should any of the following events occur during administration of the investigational agent, in the setting of a serious adverse event or adverse event that is possibly related to exendin-(9-39), the subject's treatment will be discontinued and the subject will be followed clinically.
 - i. Blood pressure instability
 - ii. Pulse instability
 - iii. Fever

Trial stopping rules:

If 2 subjects experience serious adverse events thought to be probably or definitely related to study procedures or medications we will place the study on a voluntary hold to evaluate safety and study design. The IRB, FDA, and the Safety Officer will be informed and consulted as appropriate and per local and federal regulations.

Potential study related SAEs include the following:

1. Anemia requiring hospitalization as a consequence of the amount of blood being collected in study procedures
2. Severe hypersensitivity reaction requiring hospitalization

Surveillance of subjects will be performed to permit early detection of adverse events as discussed in the Data and Safety Monitoring Plan.

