5.6.1. Data and Safety Monitoring Board

Given the nature of the study a Data and Safety Monitoring Board (DSMB) is not necessary. The attached data safety and monitoring plan include the establishment of a Safety Officer. The safety of the subjects enrolled on the study will be assessed by the Safety Officer. All SAE 's will be reviewed as they occur. Reporting requirements to the IND will be strictly adhered to. If more than one unexpected or previously undescribed serious adverse event attributable to exendin-(9-39) is observed, accrual to the protocol will be suspended. The Safety Officer will assess the risk to the subject, and a recommendation to continue with the study or close it will be made to the IRB for review. Should the decision be made to continue with the study, the modifications to the protocol, the updated assessment of risks and benefits, and a modified informed consent will be submitted to the IRB and FDA for consideration.

6. Data Handling and Record Keeping

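### After a hyperglycemia trigger, item 11b does not require the next dose to be below the triggering dose; this matters in cohort 1 and after a repeat trigger

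*Combined protocol and SAP*

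**What the plan says.** Section 3.4, item 11b, has three parts. The first is a trigger: glucose above 200 mg/dL lasting 2 hours while the infant is off dextrose. The second is the response: escalation stops and "the dosing algorithm will be modified to proceed with a dose that is 2 fold higher the previous level observed to be safe". The third is a separate sentence that stops dosing if a severe adverse event occurs. "Severe" is not defined.

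The doses to which the rule applies are in items 8 and 10. Cohort 1 of Scheme #4 is fixed in item 8: "The starting dose of exendin-(9-39) will be 1000 pmol/kg/min (0.2 mg/kg/hr". The later cohorts receive 0.6, 2 and 6 mg/kg/hr. The last scheme completed before Scheme #4 was Scheme #3: "exendin-(9-39) infused for 6 hrs at a dose of 500 pmol/kg/min (0.1 mg/kg/hr". Section 1.4 presents the cohort 1 dose as twice the highest pilot dose and describes the doses given so far as generally safe.

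The other controls are in section 5. Section 5.4 holds back each cohort until safety data from the previous one are in, and says: "Decisions to dose escalate or halt dose escalation will be based on review of these data by the investigator", together with the Safety Officer and the pharmacologist. Under section 5.5, after related serious adverse events in 2 subjects, "we will place the study on a voluntary hold to evaluate safety and study design". Section 5.6.1 adds: "If more than one unexpected or previously undescribed serious adverse event attributable to exendin-(9-39) is observed, accrual to the protocol will be suspended".

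**The concern.** Item 11b is the protocol's written response to an exaggerated drug effect in infants. Its evident purpose is to fall back to an intermediate dose. Doubling the last safe level does that only when the step up was more than 2-fold. After a step of exactly 2-fold, the rule leads back to the dose that has just met the criterion.

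The consequence would fall on later infants, because each subject has a single exendin-(9-39) infusion. They could be given the triggering dose on the authority of the rule meant to protect them, or the team could find that the rule names no dose.

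**Working it through.** **Inputs.** Scheme #3 dose 0.1 mg/kg/hr over 6 hours and Scheme #4 doses 0.2, 0.6, 2 and 6 mg/kg/hr over 9 hours (section 3.4, item 10); the 2-fold factor (item 11b).

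**Reproducing the plan's figures.** 2 × 500 = 1000 pmol/kg/min, the stated starting dose. Nine-hour totals are 0.2 × 9 = 1.8, 0.6 × 9 = 5.4, 2 × 9 = 18 and 6 × 9 = 54 mg/kg, as in the dose table.

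**Formula.** Let step = triggering dose ÷ last safe level. The 11b dose is 2 × last safe level, so

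relative change from the triggering dose = 2 ÷ step − 1.

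This is negative only when step > 2.

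**First trigger (mg/kg/hr).**

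| Cohort | Last safe | Triggering | Step | 11b dose | Change |
|---|---|---|---|---|---|
| 1, if Scheme #3 counts | 0.1 | 0.2 | 2.0 | 0.2 | 0% |
| 1, if only Scheme #4 counts | none | 0.2 | – | none given | – |
| 2 | 0.2 | 0.6 | 3.0 | 0.4 | −33% |
| 3 | 0.6 | 2 | 3.33 | 1.2 | −40% |
| 4 | 2 | 6 | 3.0 | 4 | −33% |

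**Third reading of cohort 1.** If the level meant total dose, Scheme #3 gives 0.1 × 6 = 0.6 mg/kg. Doubled, that is 1.2 mg/kg, or 1.2 ÷ 9 = 0.133 mg/kg/hr, a 33% cut from 0.2. The text does not choose among these readings.

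**Trigger at a modified dose.** The protocol does not cover this. If the formula were applied again, the last safe level would be unchanged, so the step is 0.4 ÷ 0.2 = 1.2 ÷ 0.6 = 4 ÷ 2 = 2.0. The result is 0.4, 1.2 or 4 again, a change of 0%. These figures come from extending the rule and are not protocol instructions.

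**Do other provisions set a lower dose?** Stopping escalation bars a higher dose but does not call for a lower one. Section 5.4 requires a review but names no dose. The hold in section 5.5 and the suspension in section 5.6.1 depend on serious adverse events, not on the glucose criterion, and set no dose.

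**The case against.** The strongest reply is that the rule works at every step inside Scheme #4. Those steps are 3.0-, 3.33- and 3.0-fold, and doubling the last safe level falls inside each. That stands, and it confines the point to two edge cases.

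The cohort 1 result of no reduction depends on counting Scheme #3, which is marked completed and ran for 6 hours rather than 9. That also stands. The other natural reading, however, leaves 11b without a dose.

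For a repeat trigger, a reader might infer that the protocol orders the same modified dose again. It does not. It is silent, and the decision would fall to the reviewers named in section 5.4.

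There are real backstops. The severe-event sentence in 11b stops dosing outright and is the closest of them. Since the term is undefined, it may not cover every glucose trigger; if it did, the 2-fold instruction would never operate. Glucose is checked every 30 minutes, and section 1.4 gives a typical pediatric half-life of 0.94 hours. Continuing at an unchanged dose after one reversible effect could be a defensible judgment, and a strict cap would remove that discretion. The Data Safety Monitoring Plan is listed as an attachment but is not in the text available, so it may deal with these cases.

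A reader might also infer that such a trigger is likely, because section 1.4 reports possibly drug-related Grade 3 transient hyperglycemia in 2 of 31 subjects (2 ÷ 31 = 6.5%). The documents give neither the doses nor any sign that the 11b criterion was met. Against it, section 1.4 says of 0.1 mg/kg/hr: "We have studied 2 neonates at this dose level administered over 6 hrs and did not find an effect on glucose infusion rates".

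**Conclusion.** The point holds as a minor, edge-case correction. Item 11b has no condition that the next dose be below the triggering dose. It reduces the dose by 33% to 40% after a first trigger in cohorts 2 to 4. In cohort 1 it gives no reduction if Scheme #3 is the previous safe level by infusion rate, and no dose if only Scheme #4 levels count. A trigger at 0.4, 1.2 or 4 mg/kg/hr is left unaddressed, and the formula would not lower the dose if reused.

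The stronger inference, that 11b generally fails to step down or leaves infants without protection, is not supported. Escalation stops after any trigger, a severe adverse event stops dosing, and the section 5.4 review applies. The conclusion rests on the protocol text without the Data Safety Monitoring Plan. It affects no endpoint or analysis.

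**What to change.** Add to item 11b that the next dose must be strictly below any infusion rate, in mg/kg/hr, that has met the criterion. Add that if twice the last safe level is not below that rate, dosing returns to the last safe level or stops, as decided by the investigator, the Safety Officer and the pharmacologist. Where no earlier level counts as safe, stopping is the only option left. Saying whether Scheme #3 counts for cohort 1 would be a useful clarification.

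This takes two or three sentences in an amendment and adds no patients or procedures. It changes nothing for a first trigger in cohorts 2 to 4, where 0.4, 1.2 and 4 already lie below 0.6, 2 and 6. The downside is possibly a lower dose or an earlier stop in rare cases, with some loss of discretion for the reviewers.
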